#### Approach for handing missing data for secondary outcomes

As with the primary outcome, multiple imputation may be considered, using the methods described for the primary outcome for missing secondary outcomes (see section 10.2.1).

#### Sensitivity analysis for secondary outcomes

Similarly, as described for the primary outcome, multiple imputation maybe considered, and in the case where imbalances in a characteristic are noted in the treatment groups, the analysis maybe repeated adjusting for that characteristic (see section 10.2.1).

#### Adverse Events Analysis

SAE's will be reported descriptively by whether or not the first dose was taken, rather than as intention to treat.

#### 10.2.3. Subgroup analyses

Although the trial is not powered for subgroup analysis, a small number of pre-specified exploratory analyses will be undertaken on the primary outcome for subgroups of particular interest: cellulitis location (lower limb vs other), and NSAID usage at time of randomisation (user vs non-user). These analyses will be carried out by refitting the mixed effects linear regression model described for the primary outcome primary analysis (see section 10.3.2) with the addition of an interaction between the primary outcome and the subgroup of interest. Minimum numbers required to perform these analyses will be pre-specified in the SAP.

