# **10. STATISTICS AND DATA ANALYSIS**

# 10.1. Sample size calculation

Participants will be randomised on a 1:1 basis to receive dexamethasone plus usual care or placebo plus usual care. The required sample size has been calculated based on detecting a between-group difference in total pain, from baseline over the first 3 days post-randomisation, of 10 points, based on a standardised area-under-the-curve approach (on a scale of 0-100), with pain NRS collected twice-daily.

The minimum clinically important difference (MCID) in pain is 10 points, based on previously reported emergency care literature. The conservative SD estimate (30 points) is based on previous cellulitis trials reporting pain at single time points, reviewed in a recent meta-analysis. Based on these assumptions, the target standardised effect size is 0.33. This estimate of the pooled SD will be reviewed, blinded, at the end of the internal pilot phase.

191 participants in each allocated group with primary outcome data will give 90% power to detect the MCID of 10 points, assuming a standard deviation (SD) of 30 points, at the two-sided 5% statistical significance level. The recruitment target is 450 participants (225 per allocated group), allowing for up to 15% of participants not returning any pain score 24 hours after the baseline score.

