# 10.2.1. Primary outcome analysis

# General principles for primary analysis of primary outcome

An area under the curve (AUC) approach will be used to capture the primary outcome, total pain experienced over the first 3 days, including baseline. The AUC will be calculated using the trapezoidal rule, by rescaling the numerical rating pain scores (0-10) at each time point to a 0-100 scale, to give a standardised AUC on a scale of 0-100. Participants will be included in the primary intention-to-treat analysis if they contribute at least 2 out of a possible 7 pain scores, with the second pain score being

at least 24 hours after the baseline pain score. Missing pain scores will be imputed using linear interpolation, if scores are available either side of the missing pain score. If final scores are missing, then scores will be imputed using last observation carried forward, a conservative approach.

The primary outcome (pain AUC) will be analysed using a mixed effects linear regression (intention-totreat) model, adjusting for age, sex, baseline pain, severity of cellulitis, antimicrobial therapy for this episode of cellulitis prior to attending urgent and emergency care, diabetes status and severity of cellulitis (Eron Stage1 vs all other stages) as fixed effects and recruitment site as a random effect to account for potential between-site heterogeneity. From the model, the adjusted difference in means for the pain AUC between the dexamethasone and placebo group will be reported with 95% confidence interval. The unadjusted between-group difference in means with 95% confidence interval will also be reported.

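### The subgroup model in section 10.2.3 names an outcome-by-subgroup interaction instead of a treatment-by-subgroup one: a probable drafting slip that needs a one-sentence correction

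*Protocol*

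**What the plan says.** Section 10.2.1 defines the base model: "The primary outcome (pain AUC) will be analysed using a mixed effects linear regression". Its fixed effects are age, sex, baseline pain, prior antimicrobial therapy, diabetes and Eron severity, with site as a random effect. Neither cellulitis location nor NSAID use is in that list.

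Section 10.2.3 names two subgroup factors: "cellulitis location (lower limb vs other), and NSAID usage at time of randomisation (user vs non-user". It sets their status: "Although the trial is not powered for subgroup analysis, a small number of pre-specified exploratory analyses will be undertaken on the primary outcome". The model to be refitted is identified as the one "described for the primary outcome primary analysis (see section 10.3.2". The change to be made to that model is then worded as follows: "with the addition of an interaction between the primary outcome and the subgroup of interest".

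For subgroups, that section leaves one item to the SAP: "Minimum numbers required to perform these analyses will be pre-specified in the SAP". The form of the interaction is fixed in the protocol. No other section names a treatment-by-subgroup term. Section 10.3 covers interim analysis and has no subsections, so section 10.3.2 does not exist.

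**The concern.** A subgroup question asks whether the effect of dexamethasone differs between levels of a factor. In a regression, that is the coefficient of allocated group times factor. The sentence in 10.2.3 puts the outcome in the place of allocated group. The dependent variable, multiplied by the subgroup indicator, then becomes a predictor of itself, and the model has no parameter for effect modification. The wrong cross-reference means a reader cannot settle the wording by following it.

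Two pre-specified exploratory answers are at stake. The NSAID one is of natural interest: the background section regards NSAIDs as probably acting in a similar way to steroids, and section 8.9 allows their use during the trial. Pre-specification is meant to fix the model before unblinding. Here any sensible analysis must depart from the text, and the protocol gives no correct text to fall back on.

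**Working it through.** **Inputs from the protocol (section 10.1).** Difference 10 points ("The minimum clinically important difference (MCID) in pain is 10 points"); SD 30 ("The conservative SD estimate (30 points) is based on previous cellulitis trials reporting pain at single time points"); two-sided 5%; 90% power; 191 analysed per group; 450 recruited with 15% attrition.

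**Assumptions, not in the protocol.** Subgroup prevalence 30%, 50% or 80%; correlation of 0.5 between baseline and outcome; ordinary least squares without the site effect, which does not alter the algebra.

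**1. The plan's own figure.** n per group = 2(1.96 + 1.2816)² × 30² / 10² = 189.1, so 190 by the normal approximation. The t-test version gives 190.1, so 191. Then 2 × 191 = 382, and 382 / 0.85 = 449.4, so 450. The sample size reproduces. The protocol gives no figure for the subgroup analyses.

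**2. The literal model.** Let Y be pain AUC, T allocation, B standardised baseline pain and S the subgroup indicator.

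- Literal: Y = a + b·T + c·B + d·S + g·(Y×S)
- Intended: Y = a + b·T + c·B + d·S + g·(T×S)

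Where S = 1, the product Y×S is Y itself. Those participants are fitted perfectly by g = 1 with every other term cancelling, including b. Where S = 0, the data pull b towards the true effect. Least squares compromises: g lies near 1 whatever the truth, and b is pulled towards zero, more so as S = 1 becomes commoner.

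**3. Simulation.** Y = 50 - 10T + (interaction)·T×S + 15B + error, with error variance 900 - 225 = 675, so the SD within a group is about 30. N = 382, 1,000 trials per row.

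| Prevalence | True interaction | Literal: significant | Literal: g | Literal: treatment coefficient | Intended: significant | Intended: g |
|---|---|---|---|---|---|---|
| 30% | 0 | 100% | 0.794 | -7.67 | 3.4% | -0.14 |
| 30% | +10 | 100% | 0.811 | -7.00 | 40.1% | 9.86 |
| 30% | -10 | 100% | 0.785 | -8.30 | 37.4% | -9.84 |
| 50% | 0 | 100% | 0.844 | -5.80 | 5.8% | 0.09 |
| 50% | +10 | 100% | 0.857 | -5.02 | 46.0% | 9.96 |
| 50% | -10 | 100% | 0.836 | -6.60 | 46.0% | -10.16 |
| 80% | 0 | 100% | 0.932 | -2.56 | 5.0% | 0.14 |
| 80% | +10 | 100% | 0.938 | -2.09 | 34.9% | 10.66 |
| 80% | -10 | 100% | 0.926 | -3.18 | 31.7% | -9.80 |

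The literal coefficient hardly moves when the true interaction changes. The intended model holds about 5% and recovers the truth.

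**4. Power once corrected.** SE = 30·√(4/(382p) + 4/(382(1-p))). At p = 0.5 this is 6.14, and the power for a 10-point interaction is Φ(10/6.14 - 1.96) = 37%. At p = 0.2 it is 7.67, giving 26%. The simulated 32% to 46% is higher because baseline adjustment lowers the residual SD to about 26. Both agree with the protocol's statement that subgroups are not powered.

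**5. Why the main effect must be named.** Suppose only the word is swapped and S itself is left out. The treated-arm contrast between subgroup levels then has only g to go to, so g estimates the subgroup main effect plus the interaction. With an assumed 10-point pain difference between levels and no true interaction, g is expected to be 10 + 0 = 10. In simulation (1,000 trials per setting) it averaged about 10. It was falsely significant in 66%, 74% and 54% of trials at prevalence 30%, 50% and 80% with SD 30, and in 83%, 87% and 72% with an assumed residual SD of 22. With the main effect included, the rate was 4% to 6%.

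**The case against.** The strongest reply is that nobody would fit this model. An outcome on both sides of a regression is conspicuous, the evident meaning is allocated group, and section 10.2 promises a detailed SAP approved by the TSC and made public before follow-up ends. The 100% figure follows from algebra and does not describe a plausible analysis. The subgroup analyses are exploratory and unpowered, the stated emphasis is on estimation, and the broken cross-reference still names its target in words. Reporting within-level effects is ordinary SAP detail.

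Most of this stands, and it limits the consequence. It does not make the sentence right. The SAP is not at hand, so it cannot be credited with the correction, and the protocol delegates only the minimum numbers to it.

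Two stronger readings are tempting and unsupported:

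- A reader might infer that the treatment estimate is destroyed, citing the case where a -10 effect exists only in a subgroup of 70% (residual SD 22, both assumed). The literal model's treatment coefficient there is about -0.6, against -9.8 from the correct model. But -9.8 is the correct model's interaction. Its treatment coefficient is the effect in the reference level, zero by construction and about -0.05 in simulation. The fair comparison is attenuation under a uniform effect, and that depends on prevalence.
- A reader might infer that the published subgroup results will be meaningless. That assumes the slip survives the SAP, TSC review and programming, which the protocol does not show.

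**Conclusion.** The point holds as a minor but real correction. As written, section 10.2.3 specifies a model with no effect-modification parameter, whose interaction term was significant in every simulated trial regardless of the truth. Under a uniform -10 effect, the treatment coefficient in that auxiliary model falls to about -7.7, -5.8 and -2.6 at prevalence 30%, 50% and 80%. The prevalences and baseline correlation are assumptions; the 100% result did not depend on prevalence, but the attenuation does.

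The error is very likely a slip of words. The primary estimate, sample size, error rate, data collection and safety are untouched, and no confirmatory conclusion rests on these analyses.

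The omitted main effect is a separate, conditional weakness. It produces false interactions only if pain differs between subgroup levels. With an assumed 10-point difference the false-positive rate was about 54% to 74% at the protocol's SD of 30, and about 72% to 87% at a residual SD of 22.

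**What to change.** In section 10.2.3, replace the clause that describes the added term with wording such as: *adding the main effect of the subgroup variable and the interaction of allocated treatment group with that variable; the interaction estimate will be reported with its 95% confidence interval*. Change the cross-reference from 10.3.2 to 10.2.1. Check that the SAP carries the same corrected model. Treatment effects within each subgroup level can be left to the SAP.

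The cost is one sentence and one section number, best changed before unblinding. No data collection or sample-size change follows, since location and NSAID use are already recorded at baseline.

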# 10.3. Interim analysis and criteria for the premature termination of the trial

No interim analyses are planned for the trial.

The trial may be terminated early on the recommendation of DMC or funder. The TSC will make the final decision to terminate or continue the trial.

# 10.4. Participant population

The primary analysis population will include all those who were randomised to the trial, including those who were randomised to dexamethasone group, but did not receive it (Intention to Treat). Participants also need to contribute at least 2 out of a possible 7 pain scores, with the second pain score being at least 24 hours after the baseline pain score to be included.

# 10.5. Other statistical considerations

Any changes made to the SAP will be documented, including details of when the change was made (e.g. prior to data export) and whether the trial statistician was blinded to allocated group at the time of change.

# **11. ECONOMIC EVALUATION**

A full within-trial cost-effectiveness analysis (CEA) will be conducted to estimate the incremental costeffectiveness of the dexamethasone intervention as compared to placebo.

Resources and costs of providing oral dexamethasone will be established. Participant health, social care and broader societal resource use will be captured at baseline, Day 14 and Day 90 using self-report resource use questionnaires. These are based on the ModRUM core module but tailored to the study population, as informed by the PAG and trial team. Nationally-recognised UK health and social care unit costs will be applied to the resource use data.

QALYs will be estimated using EQ-5D-5L data collected at baseline and to Day 90 follow-up. The 'cross-walk' algorithm will be used to provide QALY weights from the EQ-5D-3L UK general population valuation survey, in accordance with the current 'position statement' of the National Institute of Health and Care Excellence (NICE). Descriptive statistics will summarise costs and QALYs by the dexamethasone and placebo groups. Mixed effects linear regression models will be undertaken to test for differences in costs and QALYs. In line with the SAP, these models will adjust for age, sex, baseline pain, severity of cellulitis, antimicrobial therapy for this episode of cellulitis prior to attending urgent and emergency care (yes/no) and diabetes status as fixed effects and recruitment site as a random effect to account for potential between-site heterogeneity. In addition, the cost regression model will adjust for baseline costs, and the QALY model for baseline EQ-5D-5L values. The CEA will synthesise cost and outcome data to present incremental cost-effectiveness ratios for: i) the trial primary outcome, in the form of cost of total pain prevented over 3 days post-randomisation, and for ii) the policy relevant economic endpoint, cost per quality-adjusted life-year (QALY) at Day 90 follow-up.

Sampling uncertainty will be accounted for in the analysis, and the pattern and potential mechanisms of missing data will be explored in considering multiple imputation. Cost-effectiveness acceptability curves will be presented as appropriate using the net-benefit approach. These will show the probability that the dexamethasone intervention is cost-effective (as compared to placebo) over a range of cost-per-QALY thresholds (e.g. the £20,000 and £30,000 thresholds considered by NICE). The CEA will initially be undertaken from a primary perspective of the NHS and Personal Social Services, with

broader societal perspectives considered in sensitivity analyses, informed by input from the PAG. A Health Economics Data Analysis Plan will be developed which will be fully concordant with the SAP, and the internationally-recognised CHEERs guidelines for reporting CEA studies.

# **12. DATA MANAGEMENT**

#### 12.1. Data collection tools and source document identification

The local research team will use the REDCap application provided by Exeter CTU to record participant data in accordance with the protocol, this electronic data capture system (EDC) will be the CRF. Direct data entry is preferred but in circumstances where there is difficulty accessing the internet or necessary IT equipment, paper source data worksheets may be required with subsequent data entry by the local research team.

The electronic randomisation and IMP management system is provided by Centre for Healthcare Randomised Trials (CHaRT; University of Aberdeen). IMP orders, receipt confirmation and individual pack statuses will be recorded directly in this system to ensure only available and non-expired drugs are able to be allocated by the system during randomisation. Sites will maintain locals IMP accountability logs for the purposes of monitoring and inspection (full details in pharmacy manual). Data required for randomisation will be entered into REDCap directly. When the user confirms they are ready to randomise the necessary data will be piped into the CHaRT system which will automatically randomise, and the allocated pack ID will be piped back in to REDCap for the user to check (see section 15.5 for further details on data transfer between REDCap and CHaRT).

Sites will be required to answer data queries raised by ExeCTU in a timely manner within the study database.

# 12.2. Source Data

At screening and baseline, the primary data source will be the medical notes. Where information is collected on the eCRFs (or source data worksheets, where required) and not previously recorded in the medical notes, the eCRFs and worksheets will be source data.

Participant questionnaires will be completed for patient reported outcome measures in the following ways at each timepoint:

- Baseline - completed by the participant on paper and transcribed into the study database by the study team.
- T1-T6 - completed electronically by participant via SMS survey, or completed electronically by site staff on REDCap when conducting in person/telephone follow-up.
- Day 14 & Day 90 - completed electronically by site staff on REDCap when conducting a follow-up telephone call with the participant.

If there are technical difficulties at T1-T6, Day 14 or Day 90, source data worksheets (paper questionnaires) can be used by the site team and the data transcribed into the database.

If completed electronically the trial database will form the source data, otherwise the paper questionnaire will form the source data.

The source data for the randomised allocation and the pack ID(s) allocated to the participant will be in the CHaRT randomisation system.

Medical case notes containing source data or other trial-related information should be identified by a label (or equivalent for electronic notes, where feasible), e.g. "Keep until at least dd/mm/yyyy" where the date given is at least ten years after the end of the trial.

# 12.3. Data handling and record keeping

A Data Management Plan (DMP) will be created for the trial and will be updated throughout the trial as appropriate. Work instructions will be provided to the site teams on record keeping and data entry processes. Electronic systems will be validated, tested and documented before starting recruitment.

Mobile phone numbers will be shared with our SMS service provider in order to send the follow-up texts (see section 12.4 for more details). If routine data linkage is added to the trial, this will be outlined in an amendment or a new ethics application by the trial team. In this case NHS number and date of birth may be shared with NHS Digital for the purpose of linkage (this would only be completed for participants who gave consent for this on the main trial consent form). No other information capable of identifying participants will be made available in any form to those outside the trial.

Any source data worksheets, paper questionnaires, paper consent forms and trial specific documents held by the site teams will be stored securely with access restricted and limited to delegated research staff. If these are not stored in the ISF, a note to file will be placed in the ISF to indicate their location. Any source data recorded on paper questionnaires or source data worksheets will be transcribed into the eCRF.

Please see the data protection section (15.5) for details on the electronic data capture system and how identifiable data will be stored.

# 12.4. Access to Data

Participants will be asked to consent to representatives of the Sponsor, the University of Exeter, University of Bristol, University of Cardiff or regulatory agencies (e.g. MHRA) accessing their data that is relevant to their participation in the trial.

Access to the data held at participating sites will be restricted to those who have a relevant purpose to access the data. Access will be granted to authorised representatives from the North Bristol NHS Trust as Sponsor, as well as representatives from University of Exeter and regulatory agencies e.g. MHRA, for the purposes of auditing, monitoring and inspection of the trial.

Data entered into the study database (including unredacted uploads of paper consent forms and electronic consent forms) may be accessed by authorised members of the trial team at participating sites, ExeCTU and regulatory authorities (e.g. MHRA) and collaborating organisations. Access to the database will be controlled by password protected individual user accounts. Staff will have access restricted by site, functionality and data that are appropriate for their location and role in the trial.

Participants will also be asked to consent to data being shared with the following third-party providers:

 Centre for Healthcare Randomised Trials (CHaRT, University of Aberdeen) will provide the randomisation and IMP management system. CHaRT will not receive any identifiable information but will receive the participant's trial ID and eligibility/minimisation criteria that are required for the randomisation. This system will also store the randomisation and IMP allocation data and a record of IMP pack statuses. Similarly to REDCap, access to CHaRT's system will be restricted to password protected user accounts restricted by site, functionality and data appropriate to the user's role.

- The SMS text messaging service provider will receive the participant's telephone number and the wording for the follow-up text messages. Their text messaging data centre is located in the United States. Participants will respond to follow-up text messages either by direct SMS reply which the service provider will automatically feedback into REDCap, or by a personalised survey link included in the message which would feed directly into REDCap. No other identifiable information will be shared with the SMS service provider. By linking directly into REDCap, REDCap will be used to store logs and records of communications with participants and the SMS service provider will delete their logs and not hold data after it has been fed back into REDCap.
- The IMP manufacturer will not receive or hold any participant data.

The above third parties will not be able to log into the study database.

